10.8 ADDITIONAL EVALUATIONS

- *Procedural and In-Hospital Evaluations:* The estimated blood loss volume, % of subjects receiving a blood transfusion, contrast volume, fluoroscopy time, endovascular device time, Polymer volume used, procedure time, anesthesia time and type, frequency of concomitant procedures, ICU time, time to hospital discharge, and % of subjects discharged to skilled nursing facilities or assisted living facilities who were not prior residents will be presented descriptively. Qualitative variables will be presented with rate. Quantitative variables will be presented with mean, standard deviation, median, minimum and maximum.
- *Mortality:* The proportion of subjects with mortality (all-cause and aneurysm-related) will be presented at 30 days and at each subsequent time point for which data are available (i.e., six months, and annually at years 1 through 5). A descriptive analysis and a Kaplan-Meier analysis of all-cause and aneurysm-related mortality through 30 days and for late follow-up including 30 days will be presented.
- *Major Adverse Events (MAE) Individual Components:* The proportion of subjects experiencing each category of MAE within 30 days and after 30 days at each subsequent time point for which data are available will be presented.
- *Composite Late MAEs (after 30 days):* The proportion of subjects experiencing an MAE after 30 days will be presented at each subsequent time point for which data are available. A descriptive analysis and a Kaplan-Meier analysis of the MAE composite will be

presented for follow-up through 30 days and for late follow-up including 30 days. The descriptive analysis will present the rates for the composite MAE and each individual adverse event that is part of the composite.

- *Aneurysm Rupture*: The proportion of subjects experiencing a rupture of the aneurysm will be presented at 30 days and at each subsequent time point for which data are available.
- *Conversion to Open Repair*: The proportion of subjects undergoing surgical conversion to open repair will be presented at 30 days and at each subsequent time point for which data are available.
- *Serious Adverse Events (SAEs)*: The proportion of subjects experiencing an SAE will be presented descriptively by time point.
- *Non-serious AEs*: The proportion of subjects experiencing a non-serious AE will be presented descriptively by time point.
- *Device Performance*: A descriptive analysis of the following will be done based on Core Lab evaluations at 30 days and at each subsequent time point for which data are available. A determination will be made from the data as to whether any observation was associated with an SAE or device malfunction.
- *Luminal Thrombus Requiring Intervention*: any endovascular surgical intervention after completion of the Nellix System implant for resolution of endograft thrombosis.
- *Aneurysm Sac Changes*: The changes in aneurysm sac (vessel) diameter from the first post-operative CT evaluation will be presented at each subsequent follow-up. The maximum diameter parameter will be used for the analysis because it is the basis for comparison to other studies with endografts. For each follow-up interval, the number and percent of subjects with increased sac diameter ($>5\text{mm}$), stable sac diameter ($\leq 5\text{mm}$), or decreased sac diameter ($>5\text{mm}$) will be presented.
- *Incidence of Migration*: Core Lab reported stent distal movement $>5\text{mm}$ from the original implant location relative to the center of the distal renal artery.
- *Incidence of Clinically Significant Migration*: Core Lab reported stent distal movement $>10\text{mm}$ from the original implant location relative to the center of the distal renal artery resulting in an intervention or in a serious complication.
- *Incidence of Endoleak*: The occurrence of endoleak (any type or location, new and persistent) will be presented descriptively at each follow-up.
- *Incidence of Stent Occlusion*: The occurrence of stent occlusion will be presented descriptively at each follow-up. Renal Function Evaluations: A descriptive analysis of renal function will be done based on serum creatinine levels and calculated estimated glomerular filtration rate (eGFR) at 30 days and at each subsequent timepoint for which data are available. Renal dysfunction will be defined as a reduction in eGFR of $>30\%$ from the preoperative value.
- *Nellix Implant Patency and Integrity*: A descriptive analysis of stent patent luminal flow, absence of stent fracture, kinking, or occlusion, and absence of device failure will be determined by contrast-enhanced CT scan, as assessed by the independent core laboratory at 30 days and at each subsequent time point for which data are available. A determination

will be made from the data as to whether the occurrence was associated with an SAE or device malfunction.

- *Secondary Endovascular procedures:* A descriptive analysis of secondary endovascular procedures for resolution of endoleak (Type I or III), device occlusion, migration, aneurysm sac expansion, and/or a device defect (including infection) will be done at 30 days and at each subsequent time point for which data are available.

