5. STUDY POPULATION

5.1. PRIMARY INVESTIGATION

Up to 30 sites in the EU, Canada, and the United States will enroll up to 180 subjects including 30 Roll-in subjects and up to 150 patients in the Intention to Treat Pivotal Cohort for endpoint analysis. Total enrollment at a single site is restricted to 15% of the Pivotal Cohort. Following investigator training, each PI will commence patient screening and enrollment under approval per applicable national and local clinical trial requirements* and complete a minimum of one (1) successful Nellix case (Roll-in) in their training phase. This training period may be modified at the discretion of Endologix. Physicians will be directly supervised in each case by designated Endologix staff.

Pivotal Cohort: Up to 150 subjects will be enrolled at a maximum of 30 sites in the US and the EU. This includes the statistically justified sample size of 132 plus an allowance for deviations from assumptions.

Roll-In Cohort: One (1) roll-in subject may be enrolled per site, therefore a maximum of 30 enrolled in the study, to allow for Investigator(s) to receive additional training on the Nellix System. Any roll-in subjects will be screened, consented, treated and followed identically to the main study cohort. However, the roll-in cohort of this study will be evaluated separately.

* Commercially approved clinical trial requirements in the EU (CE Mark), IDE approval in the US, and ITA approval in CA

Confidential. This document and the information contained herein may not be reproduced, used or disclosed without written permission from Endologix, Inc.

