5.4. EXCLUSION CRITERIA

A patient who meets ***none of the following*** criteria potentially ***may be included*** in the study:

1. Life expectancy <2 years as judged by the Investigator;
2. Psychiatric or other condition that may interfere with the study;
3. Participating in another clinical study;
4. Known allergy or contraindication to any device material;
5. Coagulopathy or uncontrolled bleeding disorder;
6. Ruptured, leaking or mycotic aneurysm;
7. Serum creatinine (S-Cr) level >2.0 mg/dL;†
8. CVA or MI within three months of enrollment/treatment;
9. Aneurysmal disease of the descending thoracic aorta;
10. Clinically significant mural thrombus within the proximal landing zone (minimum 10mm) of the infrarenal non-aneurysmal neck (>5mm thickness over >50% circumference);
11. Connective tissue diseases (e.g., Marfan Syndrome);
12. Unsuitable vascular anatomy that may interfere with device introduction or deployment;
13. Pregnant (female of childbearing potential only).

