8.8.7. Adverse Event Definitions

The following event definitions will be applied during this study.

- *Death:* Any death occurring during the study period, regardless of cause.
 - *Aneurysm-related death* is defined as any death occurring within 30 days from the date of the procedure, regardless of cause, and death due to aneurysm rupture or following any procedure intended to treat the aneurysm.
 - *Cardiac-related death* is defined as death due to arrhythmia, heart failure (including cardiogenic shock), or myocardial infarction.
 - *Pulmonary-related death* is defined as death due to pulmonary edema, respiratory failure, or pulmonary embolism.
 - *Vascular-related death* is defined as death due to stroke, cerebral hemorrhage, or other clear vascular event that is not categorized as cardiac-related or pulmonary-related.
 - *Other* is to be used to identify a death due to any event that cannot be clearly categorized as above, but where some information is available.
 - *Unknown* is to be used to identify a death where no information is available.
- *Procedural Technical Failure* is defined as a failure of the Nellix system to be delivered and deployed, such that the procedure is not completed, or the device failure results in a serious complication, or a residual endoleak occurs that cannot be resolved during the index procedure and is still present at the 30 day CT as read by the Core Lab.
- *Major Adverse Event:* An event occurring during the study that meets one of the following criteria:
 - *All-Cause Death* (see above);
 - *Bowel Ischemia:* the lack of adequate blood flow to the intestines that requires intensification of medical therapy or surgical/endovascular intervention;

- *Myocardial Infarction*: the presence of raised levels of one or more cardiac biomarkers in comparison to local laboratory reference ranges;
- *Paraplegia*: Paralysis of the lower extremities inclusive of the lower trunk;
- *Renal Failure*: the need for temporary or permanent dialysis or $>0.5\text{mg/dL}$ increase in pre-operative serum creatinine level at two consecutive intervals;
- *Respiratory Failure*: pneumonia or respiratory failure requiring ventilator support beyond 24 hours post-procedure;
- *Stroke*: a sudden development of neurological deficit due to vascular lesions of the brain such as hemorrhage, embolism, or thrombosis that persists for >24 hours;

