10.7.2 Sample Size

The primary trial effectiveness variable is the Treatment Success rate at one year post-operatively. Treatment Success is a composite of clinically-relevant outcomes, including procedural technical success and freedom from: aneurysm rupture; conversion to open repair; Type I endoleak at 12 months; Type III endoleak at 12 months; clinically significant migration; aneurysm sac enlargement; or secondary endovascular procedure up to 12 months for resolution of Type I or III endoleak, device occlusion, migration, aneurysm sac expansion and/or a device defect.

The sample size is obtained by using the exact binomial distribution using PASS 2008. A sample size of 132 subjects at one year in the study population will have 80% power against a null performance goal of 80% if the proportion of Treatment Success is 88% or higher. It is estimated that the rate of Treatment Success will be greater than 88%.

It is anticipated that the drop-out rate of the trial will be 12% or less. Because the larger of the two sample sizes after adjustment for loss to withdrawal is the one for effectiveness, a minimum

of $132/0.88 = 150$ subjects will need to be recruited for this study. Thus to allow for deviations from assumptions, 150 subjects will need to be recruited for this study.

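### Kaplan-Meier for aneurysm-related mortality in section 10.8 overstates the five-year risk modestly, because later deaths from other causes are competing events; the 30-day figure is unaffected

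*Combined protocol and SAP*

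**What the plan says.** The mortality item in section 10.8 plans two summaries for both all-cause and aneurysm-related death. The first is a simple proportion: "The proportion of subjects with mortality (all-cause and aneurysm-related) will be presented at 30 days", then at later time points ("six months, and annually at years 1 through 5"). The second is "a Kaplan-Meier analysis of all-cause and aneurysm-related mortality through 30 days and for late follow-up". The denominator of the later proportions is not defined beyond the availability of data.

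Section 8.8.7 defines aneurysm-related death as "any death occurring within 30 days from the date of the procedure, regardless of cause, and death due to aneurysm rupture", or a death after a procedure to treat the aneurysm. It lists cardiac, pulmonary, vascular, other and unknown deaths as further categories; cardiac-related death, for example, is "death due to arrhythmia, heart failure (including cardiogenic shock), or myocardial infarction".

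No section mentions competing risks or cumulative incidence. The synopsis promises suitable methods for the additional evaluations in general terms, which does not displace the method that 10.8 names.

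**The concern.** Kaplan-Meier is the right estimator for all-cause mortality. For a cause-specific death it answers a different question. A subject who dies of another cause is censored and leaves the risk set, and those still under observation then stand in for that subject, as if he or she could still have died of the aneurysm. One minus the curve is therefore at or above the proportion of subjects who actually die an aneurysm-related death, and the gap grows as other-cause deaths accumulate.

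Aneurysm-related mortality to five years is a named evaluation of the device. A reader will take the five-year value as the share of patients lost to the aneurysm. The same report will also carry a simple proportion that can differ from the curve, with no stated reason for the difference.

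**Working it through.** The plan states no aneurysm-related mortality rate, so there is no figure to reproduce. The check asks which time points are affected, and by how much.

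**Inputs from the documents**
- Estimator and horizon: Kaplan-Meier, to year 5 (10.8).
- Event: every death to day 30; after that, only deaths from rupture or following a procedure to treat the aneurysm (8.8.7). I read the last limb as meaning treatment after the index procedure. If it included the index procedure, every death would qualify and the 30-day rule would be redundant.
- Cohort: "Up to 150 subjects will be enrolled at a maximum of 30 sites in the US and the EU" (5.1).
- Other-cause mortality: not given. The only related entry is the exclusion "Life expectancy <2 years as judged by the Investigator" (5.4), against five years of follow-up.

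**Assumptions (mine, not the documents')**
- Other-cause mortality at five years, F2: 20, 30 or 40%.
- True aneurysm-related mortality at five years, F1: 3 or 5%.
- Part of F1 falling in the first 30 days, p: 0, 1 or 2 percentage points.
- Constant cause-specific hazards after day 30.

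**At 30 days.** Every death is an event by definition, so nothing competes and the bias is zero.

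**At five years.** Let S = 1 − F1 − F2 be the proportion alive. Of the deaths after day 30, the aneurysm-related share is w = (F1 − p)/(F1 − p + F2). With constant hazards,

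1 − KM = 1 − (1 − p) × [S/(1 − p)]^w

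Example with F1 = 5%, p = 1 point, F2 = 30%: S = 0.65, S/(1 − p) = 0.65/0.99 = 0.6566, and w = 0.04/0.34 = 0.1176. Then 1 − KM = 1 − 0.99 × 0.6566^0.1176 = 5.78%, an excess of 0.78 points or 15.6%.

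Value shown by Kaplan-Meier (relative overstatement):

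| True rate | Within 30 days | Other-cause 20% | 30% | 40% |
|---|---|---|---|---|
| 3% | 0 points | 3.35% (11.7%) | 3.58% (19.2%) | 3.85% (28.2%) |
| 3% | 1 point | 3.24% (7.9%) | 3.39% (12.9%) | 3.57% (19.0%) |
| 3% | 2 points | 3.12% (4.0%) | 3.19% (6.5%) | 3.29% (9.6%) |
| 5% | 0 points | 5.59% (11.8%) | 5.97% (19.4%) | 6.43% (28.5%) |
| 5% | 1 point | 5.48% (9.5%) | 5.78% (15.6%) | 6.15% (23.0%) |
| 5% | 2 points | 5.36% (7.2%) | 5.59% (11.8%) | 5.87% (17.4%) |

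At an assumed 10% other-cause mortality the overstatement is about 5% with no early deaths and about 2 to 4% with 1 or 2 points early.

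**Against sampling error.** The binomial standard error at n = 150 is √(0.03 × 0.97/150) = 1.39 points at 3% and √(0.05 × 0.95/150) = 1.78 points at 5%. The largest excesses in the table are 0.85 and 1.43 points.

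**Simulation** (n = 150, 2,000 runs; assumed 1% mortality at 30 days, then 1% per year aneurysm-related and 5% per year other-cause):

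| Dropout | 1 − KM | Aalen-Johansen | Simple proportion, all enrolled |
|---|---|---|---|
| None | 5.82% | 5.28% | 5.28% |
| 3% per year | 5.70% | 5.16% | 4.89% |

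The standard deviation of the Aalen-Johansen estimate was 1.85 points with dropout, against a bias of about 0.5 points.

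**The case against.** The strongest reply is that this is a choice of estimand. Kaplan-Meier for a cause-specific death targets a net risk under independent censoring, and 10.8 does not say that the curve estimates the proportion who die of the aneurysm. It also does not say what is censored; that is inferred from the standard method. Both points are fair. But a net risk needs an untestable independence assumption and is not what most readers will take a mortality figure to mean. If it is intended, the plan should say so.

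A second reply is that the simple proportion in the same item already gives the needed figure. That holds only without dropout and with all enrolled subjects as the denominator. Section 10.7.2 allows for losses ("It is anticipated that the drop-out rate of the trial will be 12% or less"), and the denominator is undefined, so the proportion is a partial cross-check. For the same reason the size of any mismatch between the two summaries cannot be predicted.

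A third reply is that nothing is decided on this estimate. That stands in full: there is no hypothesis or threshold, both primary endpoints use other methods, and an error against the device cannot produce a falsely favourable result.

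Three stronger readings are tempting but unsupported. A reader might take 12 to 28% as the expected overstatement. That range requires that no aneurysm-related death falls in the first 30 days, although 8.8.7 counts every death in that window, so it is the top of the plausible range. A reader might also infer that the documents describe a population with heavy other-cause mortality; they give no rate. Finally, one might infer that the trial's safety conclusion is at risk. The primary safety endpoint is measured at 30 days and does not use this curve.

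**Conclusion.** The point holds as a minor one. The direction is certain if other-cause deaths after day 30 are censored, as a standard Kaplan-Meier analysis would do. The size rests on assumed rates. For a true five-year rate of 3 to 5% and other-cause mortality of 20 to 40%, the relative overstatement is about 12 to 28%, 8 to 23% or 4 to 17% as 0, 1 or 2 points of the total fall within 30 days, and it is smaller if other-cause mortality is lower. In absolute terms it is under about 1.5 points and below one standard error at 150 subjects in every case computed. Constant hazards matter too: if aneurysm-related deaths cluster late, the overstatement is larger than shown; if they cluster early, it is smaller. The case for acting is that a bias of known direction can be removed almost without cost, not that any study conclusion depends on it.

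**What to change.** In the mortality item of section 10.8:
- Estimate aneurysm-related mortality by the cumulative incidence function (Aalen-Johansen), with every death not classed as aneurysm-related under 8.8.7 as a competing event. State explicitly that this includes deaths of unknown cause.
- Keep Kaplan-Meier for all-cause mortality.
- If wanted, keep a Kaplan-Meier curve of aneurysm-related mortality as a labelled secondary display, for comparison with other endograft reports.
- Define the denominator of the accompanying proportions.

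The cost is a line or two of SAP wording and one extra analysis in standard software. No new data are needed, because 8.8.7 already classifies deaths by cause. The downside is that the main display becomes less directly comparable with reports that use Kaplan-Meier, which the secondary display addresses.

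### Section 10.8 gives late device failures only per-time-point summaries with no stated denominator, so five-year cumulative risk is not estimated

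*Combined protocol and SAP*

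**What the plan says.** Section 10.8 of the combined protocol and SAP deals with late outcomes in two ways.

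- **Time-to-event.** Kaplan-Meier analysis is named for all-cause and aneurysm-related mortality and for the MAE composite. Section 10.6.3 also names it for MAE at 30 days.
- **Per time point.** For rupture, the proportion of subjects with a "rupture of the aneurysm will be presented at 30 days and at each subsequent time point for which data are available". For conversion: "The proportion of subjects undergoing surgical conversion to open repair will be presented at 30 days and at each subsequent time point". For endoleak: "The occurrence of endoleak (any type or location, new and persistent) will be presented descriptively at each follow-up". Stent occlusion has the same form. Migration falls under Device Performance, where the plan is: "A descriptive analysis of the following will be done based on Core Lab evaluations at 30 days and at each subsequent time point". Sac change is given as number and percent in each follow-up interval. For secondary procedures the plan is "A descriptive analysis of secondary endovascular procedures for resolution of endoleak (Type I or III), device occlusion, migration, aneurysm sac expansion" and/or a device defect, and this "will be done at 30 days and at each subsequent time point for which data are available".

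None of these device failures is an MAE component (sections 6.1 and 8.8.7), so the MAE curve does not capture them. Section 10.8 states no denominator, censoring rule or treatment of death for any of them.

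**The concern.** Follow-up runs to five years, but the primary effectiveness endpoint stops at one. Section 10.8 is therefore the only planned analysis of durability in years 2 to 5. Section 8.6 records that the sponsor reported to the FDA, from two-year data, more migration, Type IA endoleak and sac enlargement than it had expected. The natural question is what share of implanted patients will have had each failure by five years.

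A summary at each visit does not answer that. Over five years some subjects die and some are lost. The result then depends on whether the numerator is new, current or ever-failed subjects, and on whether the denominator is everyone enrolled or those still attending. The plan fixes neither. It uses time-to-event methods for mortality and MAE and does not explain why device failure is treated differently.

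**Working it through.** **Is the gap closed elsewhere?**

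- Section 10.2: imputation and tipping-point analyses serve the primary endpoints. Tabulating eligible and compliant subjects at each visit shows attrition but does not adjust for it.
- Section 10.3: adverse events within six months and one year are counted cumulatively to days 180 and 365. No rule is given for years 2 to 5. Cox regression is mentioned only as a general supportive tool and would not by itself give a cumulative risk.
- Section 8.5.4: follow-up ends at 30 days for non-implant or conversion at the index procedure. The current text has no exit rule after a late failure.
- Sections 8.4 and 8.5.6: six-monthly follow-up, including CT, is recommended for subjects who have failed or are at risk. How often a subject is scanned therefore depends on failure or risk status.

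**Figures in the documents.** No five-year failure, death or loss rate is stated. The only attrition figure is the drop-out of 12% or less in section 10.7.2. There it inflates the one-year sample size, 132/0.88 = 150, which reproduces.

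**Illustration.** Assume constant yearly hazards: f for first failure, m for death, c for loss. At five years:

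- A, cumulative incidence with death competing: f/(f+m) × (1 − e^(−5(f+m)))
- B, observed failures over all enrolled: f/(f+m+c) × (1 − e^(−5(f+m+c)))
- C, ever-failed among five-year attenders, if failed subjects keep attending at the same death and loss rates: 1 − e^(−5f)

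With f = m = c = 0.05:

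- A = 0.5 × (1 − e^(−0.50)) = 19.7%
- B = (1/3) × (1 − e^(−0.75)) = 17.6%
- C = 1 − e^(−0.25) = 22.1%

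With f = 0.08 and m = c = 0.05:

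- A = (0.08/0.13) × (1 − e^(−0.65)) = 29.4%
- B = (0.08/0.18) × (1 − e^(−0.90)) = 26.4%
- C = 1 − e^(−0.40) = 33.0%

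In this model C is also what one minus Kaplan-Meier gives when deaths are censored. Extending Kaplan-Meier to device failures would therefore still sit somewhat above A.

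**Sensitivity to loss.** Take f = 0.04 and m = 0.03, and read the 12% either as loss over five years (c = −ln(0.88)/5 = 0.0256) or as loss per year (c = −ln(0.88) = 0.1278). Here D is observed failures divided by those failures plus event-free five-year attenders, that is B/(B + e^(−5(f+m+c))).

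| Loss | A | B | D |
|---|---|---|---|
| 12% over 5 years | 16.9% | 15.9% | 20.4% |
| 12% per year | 16.9% | 12.7% | 25.5% |

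Over f = 2%, 4%, 6% and m = 3%, 6% with both loss readings, A runs from 8.2% to 24.2%, B from 6.2% to 22.8%, and D from 10.8% to 37.3%. B is below A and D above A in every case.

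**The case against.** The strongest reply is that these are descriptive additional evaluations with no hypothesis test, and that several of them are sound as they stand. A visit-level endoleak figure is a valid prevalence. Section 10.3 says confidence limits for proportions will generally be given. Kaplan-Meier for aneurysm-related mortality covers death from rupture and death after procedures to treat the aneurysm. With 150 subjects, a 95% interval around 20% is about ±1.96 × √(0.2 × 0.8/150) = ±6.4 points before attrition. That is wider than the gaps of 2.1 and 2.4 points in the 5% illustration.

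All of this stands, and it limits the point to a recommended improvement. It does not supply a five-year risk of non-fatal device failure. Nor does sampling error excuse an undefined estimand, because the interval would be centred on a different quantity depending on the denominator chosen.

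A reader might also infer more than the text supports:

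- **That denominators are subjects with data.** The phrase about available data qualifies the time point. The mortality bullet spells those points out as six months and years 1 to 5. The denominator is simply not stated.
- **That every durability outcome is a proportion.** Only rupture, conversion and sac change are specified as proportions or percents. The rest are descriptive.
- **That failed subjects leave the study.** This is documented only for failure at the index procedure. For later migration, Type IA or IB endoleak or sac enlargement, more follow-up is recommended.
- **That a year-5 new-failure rate shows a large error.** It is a one-year interval rate, and section 10.8 does not present it as a five-year risk.

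**Conclusion.** The point holds in limited form. If section 10.8 is followed exactly, five-year cumulative risk is not estimated for rupture, conversion, Type I/III endoleak, migration, sac enlargement, occlusion or secondary procedures. The visit figures may understate or overstate that risk if read as such. It would go too far to say that the plan misstates the risk in a known direction. The direction depends on a denominator that is not stated, and the size depends on rates that the documents do not give.

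Under the assumed 5% yearly rates the departure is about 2 points either way around 19.7%. At 8% failure it is 3.0 points below or 3.6 points above 29.4%. It grows with heavier loss. These figures assume constant, independent hazards and are illustrations, not predictions for this trial. The 30-day safety and one-year effectiveness tests are unaffected.

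**What to change.** In section 10.8:

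1. Keep the visit tables, label them as prevalence at that visit, and state numerator and denominator for each outcome.
2. Add cumulative incidence to five years with 95% confidence intervals for each failure type, with death as a competing event (Aalen-Johansen estimator).
3. Censor at the last informative CT for imaging outcomes and at last contact for clinical ones. Keep subjects who have failed counted as events.
4. Assign imaging events to the scheduled visit windows of section 8.5.5, so that the extra six-monthly scans do not shift event dates.

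The cost is a few more tables and figures from data already collected. No visits are added and no primary analysis changes.
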